### **Phase 2 Study Design:**

Once the Phase 1b dose escalation phase of the trial is completed and an RP2D determined, the CTSC will open the Phase 2 part of the study. Patients with

advanced CRC who have KRAS wild-type tumors will initially accrue until 9 patients are enrolled and have completed the DLT period. If the DLT rate in this CRC population does not exceed 33%, accrual will begin for patients who have KRAS mutant tumors and continue to accrue for patients who have KRAS wild-type tumors. Additional safety run-in cohorts will not be required if other doses are tested in Phase 2. Patients may be enrolled simultaneously without an observation time between patients. After the appropriate number of initial stage patients in each arm have been enrolled and followed for at least 8 weeks, an efficacy and safety analysis will be performed as described in the Statistical Analysis Plan (SAP). The CTSC will convene to review and approve proceeding with full accrual of either or both arms, or terminate either arm. Full accrual in either arm may be opened earlier by the CTSC at any point at which sufficient anti-cancer activity is observed. The CTSC may also approve further enrollment and exploration of additional alternate Phase 2 doses that may enhance efficacy.

Based on review of safety, efficacy, and PK data available from Phase 1b, the planned Phase 2 dose and schedule of Hu5F9-G4 that will be used in the Phase 2 part of this study and is shown in [Synopsis Table 3](#).

When both study drugs are given on the same visit day, Hu5F9-G4 will be administered at least 1 hour after the completion of the cetuximab administration.

Starting with Cycle 2, the Day 8 and Day 22 dosing of Hu5F9-G4 has been removed (i.e., dosing is every 2 weeks [Q2W]). Patients enrolled in the Phase 1b part of the study who have been on study for at least 8 weeks may have their dose revised to the RP2DS, at the discretion of the Investigator.

**Synopsis Table 3: Phase 2 Dose and Schedule**

Drug/Dose (Intravenous)	Dose Schedule (Day per 28-day Cycle)		
	Cycle 1	Cycle 2	Cycle 3+
Hu5F9-G4 1 mg/kg (prime)	Day 1	—	—
Hu5F9-G4 30 mg/kg (maintenance)	Days 8, 15, and 22	Days 1 and 15	Days 1 and 15
Cetuximab 400 mg/m  (load)	Day 8	—	—
Cetuximab 250 mg/m  (maintenance)	Days 15 and 22	Days 1, 8, 15, and 22	Days 1, 8, 15, and 22
Hu5F9-G4 1 mg/kg (prime)	Day 1	—	—
Hu5F9-G4 45 mg/kg (maintenance) a	Days 8, 11, 15, and 22	Days 1, 8, 15, and 22	Days 1 and 15
Cetuximab 400 mg/m  (load)	Day 8	—	—
Cetuximab 250 mg/m  (maintenance)	Days 15 and 22	Days 1, 8, 15, and 22	Days 1, 8, 15, and 22

- a If recommended by the Clinical Trial Steering Committee, other doses and schedules may be tested in Phase 2

**Clinical Trial Steering Committee**

The CTSC will oversee the conduct of the clinical trial. A representative from the Sponsor, usually the Study Medical Monitor or designee, will chair the CTSC.

The CTSC will have representation from each participating site in the study.

The CTSC will review safety and efficacy data generated during the trial and make decisions about patient recruitment, trial management, initiation of protocol specific amendments, expansion of cohorts, using higher or lower dose levels, defining any new dose cohorts, identification of the recommended dose for Phase 2 trials, including evaluation of multiple Phase 2 doses, and interim efficacy analysis decisions. The CTSC will meet at a minimum at the completion of each dosing cohort during dose escalation phase of the trial, at any protocol-specified formal interim analyses, and when emergent critical safety data are reported.

The composition, structure, and function of the CTSC are defined in the CTSC Charter.

## **Duration of Treatment**

It is anticipated that this study will take approximately 42 months to complete.

Patient participation will include screening, treatment, and follow-up. Screening will last up to 30 days before first dose of study drugs, during which time the patient's eligibility and baseline characteristics will be determined. Treatment with study drugs may be continued until an unacceptable drug-related toxicity occurs, patient refusal, or until disease progression. Post treatment, patients will be observed for disease progression and survival until death, withdrawal of consent, or the end of the study, whichever occurs first.

## **Overview of Assessments**

Assessments will be performed according to the schedules provided in Protocol Section 7 ([Table 4](#), [Table 5](#), [Table 6](#), [Table 7](#), [Table 8](#), [Table 9](#), and [Table 10](#)).

## **Planned Number of Patients**

An estimated 15 to 24 patients will be enrolled in Phase 1b, depending on dose escalation and expansion.

Phase 2 includes 2 arms, one comprising patients with KRAS mutant CRC and the other comprising patients with KRAS wild-type CRC, in which enrollment in one or both arms may be modified based on emerging data. A total of 88 patients (44 patients per arm) will be enrolled in Phase 2, assuming progression to Stage 2 for both arms.

## **Inclusion Criteria**

1. Adults  $\geq$  18 years old.
2. Histological Diagnosis

- a. Phase 1b only:

Histologically or cytologically confirmed advanced solid malignancy with an emphasis on CRC, head and neck, breast, pancreatic and ovarian cancers who have been treated with at least one regimen of prior systemic

- therapy, or who refuse systemic therapy, and for which there is no curative therapy available.
- b. Phase 2:
- KRAS Mutant CRC: Histologically confirmed advanced KRAS mutant CRC who have progressed or are ineligible for fluoropyrimidine, irinotecan- and oxaliplatin-based chemotherapy

OR
  - KRAS Wild-Type CRC: Histologically confirmed advanced KRAS wild-type CRC who have progressed or are ineligible for fluoropyrimidine, irinotecan- and oxaliplatin-based chemotherapy and who are refractory to at least 1 prior systemic therapy that included an anti-EGFR antibody, such as cetuximab, panitumumab, or others.  
Patients should have disease progression during prior anti-EGFR therapy or within 6 months of the last day of treatment with the anti-EGFR
3. Eastern Cooperative Oncology Group (ECOG) Score 0-2.
  4. For the Phase 2 part only: Disease that is measurable or assessable for response according to RECIST Version 1.1 Criteria.
  5. Laboratory measurements, blood counts:
    - Hemoglobin  $\geq$  9.5 g/dL.
    - Absolute neutrophil count (ANC)  $\geq 1.0 \times 10^9/\text{mL}$ .
    - Platelets  $\geq 75 \times 10^9/\text{mL}$ .
  6. Laboratory measurements, hepatic function:
    - Aspartate aminotransferase (AST)/alanine aminotransferase (ALT)  $< 5 \times$  upper limit of normal (ULN).
    - Bilirubin  $< 1.5 \times$  ULN or  $3.0 \times$  ULN and primarily unconjugated if patient has a documented history of Gilbert's syndrome or a genetic equivalent.

7. Laboratory measurements, renal function:  
Serum creatinine  $\leq 1.5 \times \text{ULN}$  or, if elevated, a calculated glomerular filtration rate (GFR  $> 30 \text{ mL/min}/1.73 \text{ m}^2$ ).
8. Negative urine or serum pregnancy test within 30 days before administration of Hu5F9-G4 for women of childbearing potential.
9. Females of childbearing potential must be willing to use 1 effective method of contraception during the study and continue for 4 months after the last dose of Hu5F9-G4 and 6 months after the last dose of cetuximab.
10. Males must be willing to use 1 effective method of contraception and refrain from sperm donation during the study and continue for 4 months after the last dose of Hu5F9-G4 and 6 months after the last dose of cetuximab, if the partner is a female of childbearing potential.
11. Subject has provided informed consent.
12. Must be willing and able to comply with the clinic visits and procedures outlined in the study protocol.
13. Phase 2 only:  
Willing to consent to 1 mandatory pre-treatment and 1 on-treatment tumor biopsy, unless determined to not be feasible by the Investigator (reasons include, but are not limited to, lack of accessible tumor tissue to biopsy and patient safety issues).

### **Exclusion Criteria**

1. Patients with active brain metastases (patients with stable treated central nervous system [CNS] lesions who are off corticosteroid and radiation therapy for at least 3 weeks are not considered active).
2. Prior anti-cancer therapy including chemotherapy, hormonal therapy, or investigational agents within 2 weeks or within at least 4 half-lives prior to Hu5F9-G4 dosing (up to a maximum of 4 weeks), whichever is longer. In all situations, the maximum required washout period will not exceed 4 weeks prior to the day of first treatment with Hu5F9-G4. Localized non-central nervous system (CNS) radiotherapy, previous hormonal therapy with luteinizing hormone releasing hormone (LHRH) agonists for prostate cancer,

low-dose steroids (oral prednisone or equivalent  $\leq$  20 mg per day), and treatment with bisphosphonates and RANKL inhibitors are not criteria for exclusion.

3. Prior treatment with CD47 or SIRPa-targeting agents.
4. Known active or chronic hepatitis B or C infection or human immunodeficiency virus (HIV).
5. Red blood cell (RBC) transfusion dependence, defined as requiring more than 2 units of RBC transfusions during the 4-week period prior to Screening. RBC transfusions are permitted during the Screening period and prior to enrollment to meet the hemoglobin inclusion criteria.
6. History of hemolytic anemia or Evans syndrome in the last 3 months.
7. Phase 2 only:  
Second malignancy, except treated basal cell or localized squamous skin carcinomas, localized prostate cancer, or other malignancy for which treatment was completed at least 3 years ago and for which there is no evidence of recurrence.
8. Hypersensitivity to the active substance or to murine proteins, or to any of the other excipients of cetuximab listed in [Appendix A](#).
9. Significant medical diseases or conditions, as assessed by the Investigators and Sponsor, that would substantially increase the risk-benefit ratio of participating in the study. This includes, but is not limited to, acute myocardial infarction within the last 6 months, unstable angina, uncontrolled diabetes mellitus, significant active infections, severely immunocompromised state, and congestive heart failure New York Heart Association (NYHA) Class II-IV.
10. History of psychiatric illness or substance abuse likely to interfere with ability to comply with protocol requirements or give informed consent.
11. Pregnancy or active breast feeding.
12. Positive IgG component of the direct antiglobulin test (DAT).

## **Test Product, Dose, and Mode of Administration**

Hu5F9-G4 is a humanized IgG4 monoclonal antibody that binds to human CD47 and blocks its interaction with its receptor, enabling phagocytosis of human cancer cells. Hu5F9-G4 drug product is provided in a liquid dosage form intended for intravenous (IV) infusion, supplied in single-use, 10-mL vials containing 200 mg of the antibody in a formulation of 10 mM sodium acetate, 5% (w/v) sorbitol, 0.01% (w/v) polysorbate 20, at pH of 5.0.

Erbitux® (cetuximab) is a recombinant, human/mouse chimeric monoclonal antibody that binds specifically to the extracellular domain of the human EGFR. Cetuximab is supplied at a concentration of 2 mg/mL as a 100 mg/50 mL, single-use vial or as a 200 mg/100 mL, single-use vial as a sterile, injectable liquid containing no preservatives. Cetuximab is formulated in a solution containing 8.48 mg/mL sodium chloride, 1.88 mg/mL sodium phosphate dibasic heptahydrate, 0.41 mg/mL sodium phosphate monobasic monohydrate, and Water for Injection, USP.

## **Combination Therapy, Dose, and Mode of Administration**

### **Study Endpoints**

The study objectives and endpoints are outlined above in [Synopsis Table 1](#).

### **Statistical Methods and Analyses**

All analyses will be descriptive in nature. Descriptive statistics will be provided for all safety and efficacy endpoints.

All analyses will be conducted separately for patients in Phase 1b and Phase 2 parts of the study. However, safety analyses may be conducted for patients in both Phase 1b and Phase 2. In addition, efficacy analyses will be conducted separately for the two cohorts in Phase 2.

For continuous variables, the mean, standard deviation, median, and ranges will be provided. For categorical variables, the frequency and percentage in each category will be provided along with confidence intervals for primary and secondary efficacy

endpoints. For time-to-event variables, the Kaplan-Meier (KM) estimates and corresponding two-sided 95% confidence intervals for the median and quartiles will be provided. The KM plot may also be provided. Details regarding the statistical analysis to be conducted, including the handling of missing data and patient withdrawal, will be provided in the SAP.

**Safety:** The statistical analysis of safety will be conducted for patients in the safety analysis set (SAF). Safety variables to be examined include DLTs, treatment emergent adverse events (treatment-emergent adverse events [TEAEs]): AEs worsening or occurring during or after a patient's first exposure to study drugs), vital signs, physical examinations, laboratory, receptor occupancy, and antidrug antibody assessments. Adverse events will be coded using Medical Dictionary for Regulatory Activities (MedDRA, Version 17.1 or later) and grouped by system organ class and preferred term.

**Efficacy:** Endpoints used in the efficacy analysis are ORR, DOR, DCR, PFS, OS, and TTP.

Objective response is defined as CR+PR determined by RECIST v 1.1 (primary efficacy) and iCR+iPR determined by iRECIST (secondary efficacy) separately. ORR is defined as the proportion of patients with objective response in the Efficacy Analysis Set. A sensitivity analysis of ORR will be conducted on the Per Protocol Analysis Set if more than 10% of patients in the Efficacy Analysis Set are excluded from the Per Protocol Analysis Set.

Disease control is defined as CR + PR + stable disease (SD) determined by RECIST v 1.1. DCR is defined as the proportion of patients with disease control in the Efficacy Analysis Set.

DOR is measured from when the first (objective) response is met (i.e., CR or PR) until the first date of objectively documented progressive disease. Patients who do not have objectively progressive disease will be censored at their last documented progression-free date.

PFS is measured from dose initiation until the first date of objectively documented progression disease or death. Patients who do not have objectively documented progression disease AND not died will be censored at their last documented progression-free date.

OS is measured from dose initiation until death. Patients who did not die will be censored at their last known alive date.

TTP is measured from dose initiation until the first date of objectively documented progressive disease. Patients who do not have objectively documented progressive disease will be censored at their last documented progression-free date.

**Pharmacokinetics:** PK analysis will be conducted for Hu5F9-G4 and cetuximab using the PK Analysis Set (PAS). Based on the distinct MOAs of Hu5F9-G4 and cetuximab, drug-drug PK interactions are not expected. Thus, samples for PK analysis for cetuximab will be biobanked and will be analyzed based on CTSC recommendation. Summary statistics will be presented for Hu5F9-G4 serum concentrations at each scheduled time point. Descriptive graphical plots of individual serum concentration-versus-time profiles and mean concentration-versus-time profiles will be generated.

**Dose Proportionality:** The analysis of dose proportionality will be conducted for the area under the curve (AUC) and maximum concentration ( $C_{max}$ ) of Hu5F9-G4 using a power model on log-transformed scale. The log-transformed PK parameters will each be regressed onto a fixed factor for log (dose). The 90% CI of the slope for each PK parameter will be computed from the model and presented in a summary table.

**Immunogenicity Analyses:** The rate and magnitude of anti-Hu5F9-G4 antibody positivity will be evaluated for individual patients, for all patients in the Phase 1b and 2 parts of the trial, and for the pooled patient population. **PPD**

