Because of the possibility of an initial increase in tumor burden caused by immune cell infiltration in the setting of a T-cell response (termed pseudoprogression) with immunotherapy treatment, radiographic progression defined as unconfirmed progressive disease according to iRECIST ([Seymour 2017](#)) may not be indicative of true PD. Hu5F9-G4 and cetuximab combination treatment may continue past the initial determination of disease progression according to iRECIST as long as the following criteria are met:

- No new symptoms or worsening of previous symptoms
- Tolerance of Hu5F9-G4 and avelumab
- Stable ECOG performance status
- Treatment beyond progression will not delay an imminent intervention to prevent serious complications of disease progression (for example, central nervous system [CNS] metastases)

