#### **10.3.1. iRECIST Response Assessment**

Overall response will also be assessed using iRECIST. Immunotherapeutics may result in infiltration of immune cells leading to transient increase in the size in malignant lesions, or undetectable lesions becoming detectable. The criteria are identical to those of RECIST 1.1 in many respects but have been adapted to account for instances where an increase in tumor burden, or the appearance of new lesions, does not reflect true tumor progression.

Key differences are described below. All responses defined using iRECIST criteria are designated with a prefix. iRECIST time-point and best overall responses will be recorded separately.

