#### **11.3.1.1. Objective Response Rate**

Objective response is defined as CR+PR determined by RECIST v 1.1 (primary efficacy) and iCR+iPR determined by iRECIST (secondary efficacy) separately. ORR is defined as the proportion of patients with objective response in the Efficacy Analysis Set.

A sensitivity analysis of ORR will be conducted on the Per Protocol Analysis Set if more than 10% of patients in the Efficacy Analysis Set are excluded from the Per Protocol Analysis Set.

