1 INTRODUCTION

This document outlines the statistical methods and variable definitions to be implemented during the analyses of data in evaluation of efficacy, safety and PK/ADA of the clinical trial described in the Forty Seven Inc. protocol for Study 5F9004 entitled “A Phase 1b/2 Trial of Hu5F9-G4 in Combination with Cetuximab in Patients with Solid Tumor and Advanced Colorectal Cancer” Amendment 3, dated 28 Sep 2018. Analyses of biomarker data are out of scope of this SAP.

Analysis methods specified in this document take precedence over those described in the protocol should there be any difference.

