1.2 Study Objectives and Endpoints

| PRIMARY | |
|--|--|
| OBJECTIVES | ENDPOINTS |
| 
 To investigate the safety and tolerability, and to determine the RP2DS for 5F9 in combination with cetuximab. To evaluate objective response rate (ORR) of 5F9 in combination with cetuximab in patients with KRAS mutant and KRAS wild-type CRC according to Response Evaluation Criteria in Solid Tumors (RECIST) v 1.1 (Eisenhauer 2009). | 
 DLTs and adverse events (AEs) according to National Cancer Institute Common Terminology Criteria for Adverse Events (NCI CTCAE) v 4.03. ORR using complete response (CR) + partial response (PR) as defined by the investigator according to RECIST v 1.1. |
| SECONDARY | |
| OBJECTIVES | ENDPOINTS |
| 
 To evaluate the pharmacokinetic (PK) profile of 5F9 in combination with cetuximab. To evaluate the immunogenicity of 5F9 in combination with cetuximab. To evaluate efficacy of 5F9 in combination with cetuximab by the disease-control rate (DCR), duration of response (DOR), progression-free survival (PFS), overall survival (OS), and time to progression (TTP) for patients with KRAS mutant and KRAS wild-type CRC according to RECIST v 1.1 (Eisenhauer 2009). To evaluate the ORR of 5F9 in combination with cetuximab in patients with KRAS mutant and KRAS wild-type CRC according to iRECIST guidelines (Seymour 2017). | 
 5F9 concentration versus time measurements of 5F9 in combination with cetuximab. Antidrug antibodies to 5F9 and cetuximab. DCR, DOR, PFS, OS, and TTP as defined by the investigator according to RECIST v 1.1. ORR using iCR + iPR as defined by the investigator according to the iRECIST guidelines. |

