7 CHANGES TO PROTOCOL-SPECIFIED ANALYSES

The following modifications have been made to the analyses specified in Protocol Amendment 3:

- The definition of treatment-emergent period was updated to specify an end date for each patient's reporting period to be within 30 days after the last administration of study drug or initiation of new anticancer therapy, whichever occurred first.
- Endpoint TTP will not be summarized.
- The tumor assessment based on iRECIST will not be reported.
- All enrolled patients received at least 1 dose of 5F9. Enrolled Analysis Set, Efficacy Analysis Set, and Safety Analysis Set are consolidated into All Treated Patients for all efficacy and safety analyses. Per-Protocol Analysis Set is not defined any more.

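### iRECIST response rate is listed as a secondary endpoint, but SAP Section 7 drops it without a reason, so no planned output addresses that objective

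*Protocol*

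**What the plan says.** Protocol Sections 2.1.2 and 2.2.2 make the iRECIST response rate a secondary objective and endpoint. The synopsis defines it ("Objective response is defined as CR+PR determined by RECIST v 1.1 (primary efficacy) and iCR+iPR determined by iRECIST (secondary efficacy) separately"), and Section 11.3.1.1 repeats the definition. Section 10.3.1 says how the data are kept: "iRECIST time-point and best overall responses will be recorded separately". Section 10.3.1.1 lets a partial or complete response that follows unconfirmed progression stand as the best overall response, provided progression is not confirmed at the next assessment.

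The protocol also ties treatment to these criteria. Under Section 6.1.1, "combination treatment may continue past the initial determination of disease progression according to iRECIST", subject to listed conditions. Sections 10.2.2 and 10.2.3 allow the same past RECIST 1.1 progression until a scan at least 4 weeks later confirms it, again subject to conditions.

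SAP Section 1.2 still lists the endpoint: "ORR using iCR + iPR as defined by the investigator according to the iRECIST guidelines". SAP Section 4 covers confirmed best response, response rate and PFS by RECIST 1.1, plus OS. SAP Section 7 then states: "The tumor assessment based on iRECIST will not be reported". SAP Section 1 settles which text governs: "Analysis methods specified in this document take precedence over those described in the protocol should there be any difference".

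**The concern.** Anyone following the SAP would produce nothing for an objective that the same SAP states. The endpoint is not incidental: the summary of changes for Amendment 3 says iRECIST was brought in because of possible pseudoprogression, and the treatment rules were written to match. The endpoint designed to register a response after a first reading of progression is the one removed.

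Timing adds to this. The trial is open-label with investigator-assessed response. SAP Section 7 says, in the past tense, "All enrolled patients received at least 1 dose of 5F9", so the SAP was written after patients had been treated. In the same list the merging of analysis sets is explained; the iRECIST removal is not. A reader of the final report could not tell whether the endpoint was dropped for a neutral reason, such as incomplete data, or after someone had seen the responses.

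**Working it through.** The point rests mainly on text; the arithmetic only gives its scale.

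**1. The passages side by side**

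| Question | Protocol | SAP |
|---|---|---|
| Is iRECIST response rate an endpoint? | Yes, secondary (2.1.2, 2.2.2, 11.3.1.1) | Yes, secondary (1.2) |
| Are the data to be recorded? | Yes (10.3.1) | Not addressed |
| Is it analysed? | Yes (11.3.1.1: "iCR+iPR determined by iRECIST (secondary efficacy) separately") | No (absent from 4, excluded in 7) |
| Is a reason given? | Not applicable | None |
| Which text governs? | Not applicable | The SAP (1) |

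The combined effect is a stated endpoint with no analysis.

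**2. The plan's own figure**

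Inputs (protocol 11.2, SAP 1.3): null rate 5%, alternative 15%, one-sided alpha 0.10, power 80%. An exact single-stage binomial search for the smallest n meeting both limits gives n = 44, with success at 5 or more responses:

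- P(X ≥ 5 | 44, 0.05) = 0.0675
- P(X ≥ 5 | 44, 0.15) = 0.810
- at n = 43 with the same cut-off, power is 0.793, below target

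The stated 44 per arm is reproduced. It concerns the RECIST response rate and does not change here.

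**3. Size of one patient**

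If one patient responds by iRECIST but not by RECIST 1.1, the iRECIST rate exceeds the RECIST rate by 1/m, where m is the denominator:

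- m = 44: 1/44 = 2.3 points
- m = 22: 1/22 = 4.5 points (illustrative: 44 KRAS mutant patients split evenly over the two cohorts in SAP Table 2)
- m = 15: 1/15 = 6.7 points (the interim size in protocol 11.4)

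SAP Section 4 bases the response rate on treated patients with measurable disease, while eligibility also admits disease that is only assessable. The denominator may therefore be below 44, and the step larger than 2.3 points.

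For example, 4/44 = 9.1% (exact 95% CI 2.5 to 21.7) by RECIST would become 5/44 = 11.4% (3.8 to 24.6) by iRECIST.

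**4. Could such patients occur?**

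The documents give no rate. For an assumed true rate q, P(at least one in 44) = 1 − (1 − q)^44:

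| Assumed q | P(at least one in 44) |
|---|---|
| 1% | 36% |
| 2% | 59% |
| 5% | 90% |
| 10% | 99% |

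These rates are assumptions that show the range; they are not estimates.

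**5. Confirmation rules differ**

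SAP Section 4 uses confirmed best response. The note to protocol Table 15 says its best-response scheme presumes a setting in which responses need no confirmation. A plain count of patients whose two best responses differ would mix unconfirmed responses with responses after pseudoprogression. A restored table needs one confirmation rule for both.

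**The case against.** The strongest defence is that SAP Section 1.2 merely restates the protocol's objectives and Section 7 is the proper place to declare departures. Time to progression is treated the same way: listed in 1.2, dropped in 7. The analyses are descriptive, no formal test is planned, and the primary endpoint and OS remain. All of that stands. It makes this a disclosed change, not a hidden one, but it supplies neither a reason nor a date.

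Four stronger readings are tempting, and the documents do not support them.

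- *Selective reporting took place.* The past-tense sentence in SAP Section 7 shows knowledge of dosing, not of iRECIST results. Under a common confirmation rule, iRECIST could only add responders, so leaving it out does not inflate the response rate. Only a risk is shown.
- *Responses after progression are certainly lost.* SAP Section 4 does not say whether assessments after first RECIST progression count towards best response. The loss follows from the usual rule that they do not, which is an assumption here. The recorded data would also still exist.
- *The unseen difference is large against the 10-point gap between 5% and 15%.* That gap sized the primary endpoint only, and no source gives an upper limit for the number of iRECIST-only responders.
- *Without iRECIST the benefit of treatment beyond progression cannot be judged.* A single-arm iRECIST response rate would not isolate that benefit either.

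A practical objection also has force: the endpoint arrived with Amendment 3, and the documents do not show that iRECIST assessments exist for patients assessed before it.

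**Conclusion.** The point holds in this form: a secondary endpoint stated in both documents has no analysis in the governing SAP, and its removal is declared without a reason or date. In an open-label trial with a SAP written after treatment had been given, that leaves an avoidable risk of selective reporting.

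The effect is confined to this secondary objective. RECIST 1.1 response rate, the 44 per arm and OS are untouched. The size is 2.3 points per iRECIST-only responder at a denominator of 44, and more at smaller denominators; how many such patients there would be is unknown. That scale assumes that RECIST assessments after first progression do not count towards RECIST best response, and that both criteria use the same confirmation rule. It should be corrected, but it does not threaten the primary analysis.

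**What to change.** **Preferred.** Delete the iRECIST line from SAP Section 7 and add to Section 4 one descriptive table per Phase 2 cohort giving:

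- iRECIST best overall response;
- iRECIST response rate (iCR + iPR) with its confidence interval, on the same denominator and with the same response-confirmation rule as the RECIST rate;
- the number of patients who respond by iRECIST only after RECIST progression.

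State in Section 4 that RECIST assessments after first progression do not count towards RECIST best response. RECIST 1.1 response rate stays primary.

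**If iRECIST data were not adequately collected.** Mark the endpoint as not analysed in SAP Section 1.2, give the reason and the date of the decision in Section 7, and list patients treated past RECIST progression with their later responses.

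**Cost.** The preferred route needs one table per cohort and two sentences of definition, using data the protocol already asks sites to record. Sample size and error rates do not change. The drawback is a secondary result that may rest on very few patients. The alternative needs a short text change and one listing.
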